10.2.3.5. Dose and/or Interval Modification Following Bleeding Episodes

See [Section 10.2.3.5](#) for guidance on dose and/or interval modification.

10.2.4. Inhibitor Testing

Subjects will be tested for inhibitor and anti-rFIXFc antibody formation at each clinic visit. Samples for anti-rFIXFc antibody testing (see [Section 10.2.5](#)) will be collected at the same timepoint when any samples are collected for inhibitor testing, including confirmatory and

CONFIDENTIAL

The information contained herein may not be used, disclosed, or published without the written consent of Bioerativ
Therapeutics Inc

unscheduled inhibitor tests, tests for suspected inhibitor development, and as required before and after surgery. Washout prior to sample collection for inhibitor testing should be at least 72 hours. Testing for inhibitors must also be conducted at ED Milestone Visits, as described in Section 4.2.2.2. If these do not align with a scheduled study visit, an additional visit must be scheduled to complete this testing. Additional unscheduled testing for inhibitors may be performed if required by local standards of care, and inhibitor test results must be recorded on the eCRF.

Testing for inhibitors must also be performed 2 to 4 weeks prior to elective major surgery, preoperatively, postoperatively, and at the Last Postoperative Visit (see Section 4.2.3). For minor surgeries, testing for inhibitors will only be performed if indicated by the nature of the procedure, according to local standard of care.

A valid inhibitor test result is required from the ET/EOS Visit. An unscheduled visit may be required to repeat inhibitor testing under this protocol if the ET/EOS Visit inhibitor test is not evaluable, or to obtain samples to confirm a positive inhibitor test result.

In addition, if inhibitor development is suspected at any time during the study (e.g., the expected plasma FIX activity levels are not attained or if bleeding is not controlled with an expected dose), the subject will be tested for inhibitors by the central laboratory.

A positive inhibitor test result is defined as an inhibitor test result of ≥ 0.60 BU/mL that is confirmed by a second test result of ≥ 0.60 BU/mL from a separate sample, drawn 2 to 4 weeks following the original sample. Both tests must be performed by the central laboratory using the Nijmegen-modified Bethesda assay.

A low titer inhibitor is defined as a positive inhibitor test with a result of ≥ 0.60 and < 5.00 BU/mL. A high titer inhibitor is defined as ≥ 5.00 BU/mL. Subjects with discrepant inhibitor test results (initial low titer result followed by high titer result or initial high titer result followed by low titer result) should have repeat inhibitor testing performed by the central laboratory from a separate sample, drawn 2 to 4 weeks following the previous sample. If 2 of 3 test results are < 5.00 BU/mL, the inhibitor is considered low titer. If 2 of 3 test results are ≥ 5.00 BU/mL, the inhibitor is considered high titer.

10.2.5. Anti-rFIXFc Antibody Testing

At the same timepoints that samples are drawn for inhibitor testing (see Section 10.2.4), blood samples will be collected for anti-rFIXFc antibody [REDACTED] testing, including back up and archiving samples. Anti-rFIXFc antibody samples will be collected when inhibitor samples are collected for confirmatory and unscheduled inhibitor tests, tests for suspected inhibitor development, and as required before and after surgery. Samples may also be collected and archived at the time of any clinical event deemed relevant to inhibitor or anti-rFIXFc antibody testing. [REDACTED]

CONFIDENTIAL

The information contained herein may not be used, disclosed, or published without the written consent of Bioverativ Therapeutics Inc

10.2.6. Immune Tolerance Induction

10.2.6.1. Inhibitor Subgroup

Subjects developing positive inhibitors following exposure to rFIXFc study drug will be assigned to the Inhibitor Subgroup. Subjects with confirmed or suspected inhibitors may receive bypassing agents. For more information on the use of bypassing agents see Section 10.2.6.4.

10.2.6.2. Low Titer Inhibitors

Subjects developing positive low titer inhibitors will continue on study at the same or higher dose per injection of rFIXFc at the discretion of the Investigator. These subjects will continue with the schedule of assessments in Section 4.2.2.1 and Section 4.2.2.2.

If the Investigator determines that bleeding is no longer reliably controlled with rFIXFc in a subject with a positive low titer inhibitor, the subject will be eligible for ITI (see Section 10.2.6.4). If the subject declines to undergo or continue ITI, they will be withdrawn from the study. Subjects undergoing an ITI regimen will follow the schedule of assessments in Section 4.2.4, in addition to any other ITI regimen-specific assessments required.

10.2.6.3. High Titer Inhibitors

Subjects developing positive high titer inhibitors will be eligible for ITI (see Section 10.2.6.4). If the subject declines to undergo or continue ITI, they will be withdrawn from the study. Subjects undergoing an ITI regimen will follow the schedule of assessments in Section 4.2.4, in addition to any other ITI regimen-specific assessments required.

10.2.6.4. Use of Bypassing Agents

Subjects with confirmed or suspected inhibitors may receive bypassing agents (aPCC [FEIBA] or rFVIIa [NovoSeven]) at the discretion of the Investigator and within labeled dosing recommendations for the specific bypassing agent. The Investigator may prescribe bypassing agents for active bleeding or if there is a high clinical suspicion of bleeding or potential for bleeding. When possible, bleeding should be confirmed via physical examination and/or imaging prior to administration of a bypassing agent; Confirmation of bleeding should not cause any unnecessary delay in the start of treatment, as judged by the Investigator. In the event of an emergency, prior consultation with the Investigator is not required before administration of a bypassing agent; however, the Investigator must be notified of such use.

In subjects with low-titer inhibitors, bleeding events may be controlled with increased doses of replacement FIX to overwhelm the inhibitor by antigen excess. In subjects with high-titer inhibitors, bleeding may be treated with bypassing agents, which can bypass FIX inhibition. During the study, the Investigator will determine if increased doses of replacement FIX or use of bypassing agents is appropriate.

During ITI treatment, subjects may also receive bypassing agents as needed for active bleeding or if there is a high clinical suspicion of bleeding or potential for bleeding. The use of bypassing

CONFIDENTIAL

The information contained herein may not be used, disclosed, or published without the written consent of Bioerativ
Therapeutics Inc

agents in the setting of ITI requires awareness of FIX activity levels and close monitoring for cessation of bleeding events.

It is recommended that Investigators discontinue the use of bypassing agents once the inhibitor titer is <0.6 BU/mL (negative titer, or values considered negative per local laboratory reference) or once rFIXFc provides sufficient hemostatic control, as judged by the Investigator.

The prophylactic use of bypassing agents in subjects with confirmed or suspected inhibitors must be communicated to the Sponsor Medical Monitor with documentation of rationale.

All use of bypassing agents must be documented in the appropriate section of the eCRF.

10.2.6.5. Immune Tolerance Induction Therapy

Subjects who develop a positive low titer inhibitor that cannot be adequately managed with rFIXFc or who develop a positive high titer inhibitor (≥ 5.00 BU/mL) will be eligible to undergo ITI with rFIXFc. The Medical Monitor will work with the Investigator to ascertain an established ITI regimen of the Investigator's choice, using rFIXFc. The ITI regimen plan must be approved for each subject by Bioverativ's Study Medical Director. The ITI regimen can be modified during this study, but requires re-approval by Bioverativ's Study Medical Director.

In order to use rFIXFc in an ITI regimen plan, the subject or their parents/legal guardians must sign a separate consent and the subject must provide assent, as applicable, at or prior to the Pre-ITI Assessment Visit (ITI Week 0).

rFIXFc will be provided for a period of up to 24 months under an ITI protocol. The 24-month duration is based on data from the North American Immune Tolerance Registry, which demonstrated a median time to completion of therapy of 11.6 months [Dimichele 2009].

- The ITI regimen must provide adequate oversight to detect and manage potential complications associated with ITI in FIX-deficient subjects, including nephrotic syndrome and severe allergic reactions. Please see the Schedule of Events for the ITI Visits (Section 4.2.4) for procedures to be performed during the ITI treatment period.

[REDACTED]

[REDACTED]

[REDACTED]

[REDACTED]

CONFIDENTIAL

The information contained herein may not be used, disclosed, or published without the written consent of Bioverativ Therapeutics Inc

[REDACTED]

IR calculations will be performed on results obtained from the predose and postdose FIX activity samples collected under the following conditions for both the initial and the confirmatory IR assessment:

- The subject must be in a non-bleeding state, after at least a 72-hour washout.
- At the clinic, a predose FIX activity sample will be collected within 30 minutes prior to the start of injection.
- An rFIXFc dose of 50 IU/kg will be given. The actual potency shown on the vial must be used to calculate the units of rFIXFc and the volume to inject, as described in Section 10.1.1.
- A postdose FIX activity sample will be collected 10 (\pm 5) minutes after the end of the rFIXFc injection.

The reference IR value (expected recovery), which is the basis for the second criteria for complete ITI success, is defined below:

- [REDACTED]
- [REDACTED]
- [REDACTED]
- [REDACTED]
- [REDACTED]

If the criteria for success have not been met, the subject may remain on ITI at the discretion of the Investigator, up to a total duration of ITI of 24 months, at which point the subject will be required to perform the assessments of the ET/EOS Visit for ITI (see Section 4.2.4).

Subjects who choose to discontinue ITI prior to meeting the criteria for successful immune tolerance will perform the assessments of the ET/EOS Visit for ITI (see Section 4.2.4) and then be withdrawn from the study.

CONFIDENTIAL

The information contained herein may not be used, disclosed, or published without the written consent of Bioerativ Therapeutics Inc

10.2.6.6. Treatment of Bleeding Episodes During Immune Tolerance Induction Therapy

At the Investigator's discretion, activated prothrombin complex concentrates, recombinant activated coagulation factor VII, and rFIXFc can be used to treat active bleeding or to provide surgical hemostasis during ITI.

Use of immunomodulatory agents during ITI is allowed at the Investigator's discretion.

10.2.7. Surgery

Minor surgery is allowed at any time during the study. Major surgery will only be allowed in the study after the subject has had at least 3 EDs to rFIXFc without safety concerns. If a subject needs to undergo major surgery prior to 3 EDs, they will be withdrawn from the study. The Investigator must consult with Bioverativ in advance of the surgery.

All major surgeries must take place in a center that can provide study treatment, trained study personnel, postoperative assessments, and hematological consult by the Investigator or Sub-Investigator. If surgery does not take place in such a setting, the subject will be withdrawn from the study.

In addition, subjects who require major surgery may receive rFIXFc if:

1. The surgery occurs within the contracted Institution for the study and/or a separate agreement has been executed, permitting the use of study drug and Bioverativ's rights to data generated in the study at an alternative Institution deemed appropriate by the Principal Investigator or designee.
2. The Investigator and/or appropriate qualified/licensed delegate is available to:
 - a. Administer all rFIXFc doses required during surgery and during postoperative rehabilitation (if applicable).
 - b. Provide medical oversight and guidance throughout the duration of the preoperative and the intraoperative periods.

Surgeries, elective or emergent, will be classified as major and minor as follows:

- Major surgery is defined as any surgical procedure in which a major body cavity is penetrated and exposed or for which a substantial impairment of physical or physiological function is produced (e.g., laparotomy, thoracotomy, craniotomy, joint replacement, or limb amputation).
- Minor surgery is defined as any surgical procedure that does not qualify as major (e.g., minor dental extractions, port placement or removal, incision and drainage of abscess, or simple excisions).

All major surgeries will be reported as SAEs, even if the surgery does not otherwise meet the definition of an SAE.

CONFIDENTIAL

The information contained herein may not be used, disclosed, or published without the written consent of Bioverativ Therapeutics Inc

Samples for determination of predose FIX activity levels and inhibitor formation will be collected prior to the dose of rFIXFc given for the surgery, and FIX recovery levels will be sampled 10 (\pm 5) minutes after the end of the rFIXFc injection.

For major surgeries, a repeat blood draw for FIX activity should be taken approximately 9 hours after the end of the injection, but may alternatively follow local standard of care for determining when the next dose of rFIXFc should be administered. While hospitalized, blood will be drawn daily to be tested at the local laboratory for FIX activity so that monitoring of the subject can occur in real time.

All doses administered in the hospital at the study site will be captured in the eCRF. The subject/parent/caregiver should not enter these doses in the EPD.

Bleeding caused directly by surgery should not be reported, although undesired or unexpected bleeding during or after surgery should be recorded on the eCRF.

10.2.7.1. Surgical Period

For all elective surgeries, subjects will begin the surgical period with their first dose of rFIXFc given for the surgery (i.e., the pre-surgery dose). This is the preoperative period of the surgery. The intraoperative period is defined as the time from when the surgery begins to the time when the surgery is completed. The postoperative period is defined as the time period following the end of surgery through the time when the subject can return to their regular pre-surgery regimen, as judged by the Investigator/Surgeon.

See Section 4.2.3 for the surgery visit schedule. Postoperative visits are only required for major surgeries. For minor surgeries, the Investigator will contact the subject/subject's caregiver after the day of surgery to determine when the subject returns to their regular pre-surgery regimen. For minor surgeries, pre-surgery assessments of FIX activity, inhibitor, and anti-rFIXFc antibody, and hematology and blood chemistry on the day of surgery are only to be performed if indicated by the nature of the procedure, according to local standard of care. The Investigator or Surgeon's assessment of response is conducted on the day of surgery for minor surgeries; for major surgeries, the assessment occurs 24 hours after surgery and at the Postoperative Visit (1 to 2 weeks after surgery).

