10.2.7.3. Rehabilitation Period

If surgery-related dosing is to be continued during postoperative rehabilitation, the dose of rFIXFc will be adjusted to achieve a trough at a sufficient level to maintain hemostasis, including during physical therapy.

Subjects will return to their pre-surgery regimen once all dosing for the postoperative period has been completed.

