16.2.2. General Methods of Analysis

All efficacy endpoints are secondary. No imputation will be applied to any missing efficacy data.

The efficacy and surgical/rehabilitation periods will be defined in the statistical analysis plan (SAP) for the purpose of determining the study periods during which data will be used for select efficacy analyses. Data on bleeding and rFIXFc consumption will be based on the efficacy period; surgical evaluations will be based on the surgical/rehabilitation period.

Analysis of efficacy endpoints that are visit-based will include data from all study visits whether or not in the efficacy period, unless that visit is coincidental with a surgical/rehabilitation period for a major surgery, in which case it would be excluded.

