##### **5.4.2.1. Adjustments Due to Surgical/Rehabilitation Periods**

For analysis purposes, the efficacy period for a given treatment regimen will be adjusted for all surgical/rehabilitation periods (major and minor). The start and end of the efficacy period for a given treatment regimen are adjusted as follows:

	Statistical Analysis Plan	Final v1.0
---	----------------------------------	-------------------

- For patients on a prophylactic regimen before the start of a surgical/rehabilitation period, the efficacy period for the prophylactic regimen continues up to the last dose (for prophylaxis or bleeding) before the start of the surgical/rehabilitation period.
- For patients on the episodic regimen before the start of a surgical/rehabilitation period, the efficacy period for the episodic regimen continues up to 1 minute before the start of a surgical/rehabilitation period.
- For patients on a prophylactic regimen following the end of a surgical/rehabilitation period, the efficacy period for the prophylactic regimen starts or re-starts at the first prophylactic dose following the end of the surgical/rehabilitation period.
- For patients on the episodic regimen following the end of a surgical/rehabilitation period, the efficacy period for the episodic regimen starts or re-starts at 00:01 on the day following the end of the surgical/ rehabilitation period.

Start and end dates/times for the efficacy period for given treatment regimens and treatment regimen changes will be adjusted for each surgery (major or minor) as necessary.

For patients on a prophylactic regimen before the start of a surgical/rehabilitation period, the interval of time between the last dose before the surgical/rehabilitation period and the start of the surgical/rehabilitation period will not be attributed to the efficacy period for the prophylactic regimen. By definition, there should not be any treated bleeding episodes in this interval of time.

For patients on a prophylactic regimen following the end of a surgical/rehabilitation period, bleeding episodes that occur after discharge from a rehabilitation facility but before the next prophylactic dose will be attributed to the surgical/rehabilitation period and hence not counted towards the annualized bleeding rate (ABR).

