#### **5.4.3. Surgical/Rehabilitation Period**

The broadest span of time for the surgical/rehabilitation period is from the first dose of rFIXFc given for the surgery (i.e., the pre-surgery dose) up to 1 minute before the first regular prophylactic dose after the last day of postoperative care/rehabilitation. Since not all patients will have these events, specific considerations for the start and end of the surgical/rehabilitation period are as follows:

	Statistical Analysis Plan	Final v1.0
---	----------------------------------	-------------------

Start of the surgical/rehabilitation period:

- If there is more than one pre-surgical dose then the first one should be selected (a pre-surgical dose can be administered the day before the surgery).
- If there is no pre-surgical dose but there is a prophylaxis dose or dose given for “OTHER” reason prior to the surgery on the day of or the day before surgery, the last of these doses should be selected.
- If there is no pre-surgical dose or a prophylactic dose the day before surgery then select the start date/time of the surgery. If the time was not recorded then select the date and impute 00:01 for the time.

End of the surgical/rehabilitation period:

- 1 minute before the first regular prophylactic dose on or after the last date among the dates for discharge from the hospital, post-operative visit 1, post-operative visit 2, and the end of rehabilitation.
- If all of the dates mentioned above are missing, then select the first prophylactic dose after the date/time for the end of surgery. If the surgery time was not recorded then select the surgery date and impute 23:59 for the time. If the end date of the surgery is missing then select the start date of the surgery and impute 23:59 for the time.
- If the patient is not on prophylactic regimen following the surgical/rehabilitation period (e.g., the patient is on episodic regimen after completing the surgical/rehabilitation period, or the patient simply received no further prophylactic doses), then the end of the surgical/ rehabilitation period is:
  - Imputed as 23:59 on the last date among the dates for discharge from the hospital, post-operative visit 1, post-operative visit 2, and the end of rehabilitation.

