#### 6.6.1.4. Consumption

The total annualized rFIXFc consumption (IU/kg) will be calculated for each patient using the following formula:

$$\text{Annualized consumption} = \frac{\text{Total IU/kg of rFIXFc during the efficacy period}}{\text{Total number of days during the efficacy period}} \times 365.25$$

The total amount of rFIXFc received will be the sum of the nominal IU/kg administered for each injection based on the units of rFIXFc as recorded from the patient's EPD and eCRF and his most recent weight.

Total annualized rFIXFc consumption per patient will be determined for the efficacy period (i.e., excluding the PK assessments and surgery/rehabilitation periods [major surgeries]). Total annualized consumption per patient will also be derived based on treatment regimen and overall.

Consumption is a secondary endpoint in this study. A description of how consumption will be summarized is described in Section 7.4.7.

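### For children on the episodic regimen after surgery, SAP 5.4.3 can close the surgical period before surgical dosing ends, and SAP 5.4.2.1 and 6.6.1.4 disagree on whether minor surgery is excluded from consumption

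*Protocol*

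**What the plan says.** **Protocol, clinical definition.** Section 10.2.7.1: "The postoperative period is defined as the time period following the end of surgery through the time when the subject can return" to the regular regimen, as judged by the investigator or surgeon. Section 10.2.7.3: "Subjects will return to their pre-surgery regimen once all dosing for the postoperative period has been completed". For minor procedures 10.2.7.1 adds two points: "Postoperative visits are only required for major surgeries", and "For minor surgeries, the Investigator will contact the subject/subject's caregiver after the day of surgery to determine when the subject returns" to the usual regimen.

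**SAP, end of the surgical/rehabilitation period (5.4.3).** If the patient is on prophylaxis afterwards, the period runs to 1 minute before the first regular prophylactic dose that follows the last of the recorded dates. If not, the end is "Imputed as 23:59 on the last date among the dates for discharge from the hospital", the two postoperative visits and the end of rehabilitation. If all four dates are missing, it is 23:59 on the day surgery ended. Major and minor surgeries follow the same rule.

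**SAP, what happens next.** Under 5.4.2.1, "the efficacy period for the episodic regimen starts or re-starts at 00:01 on the day following the end of the" surgical/rehabilitation period. That section takes both major and minor surgical periods out of efficacy time.

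**SAP, consumption (6.6.1.4).** "Total annualized rFIXFc consumption per patient will be determined for the efficacy period". The numerator adds up all injections in that period. Section 6.6 removes PK doses by type; no sentence does the same for surgical doses. The bracketed note in 6.6.1.4 on excluded surgical periods names major surgeries only.

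**The concern.** The prophylaxis branch of SAP 5.4.3 follows the clinical definition: the surgical period lasts until regular dosing resumes. The episodic branch has no equivalent. It depends on administrative dates and ignores both the last surgical injection and the return-to-regimen date that the investigator is asked to establish.

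After minor surgery there is normally no postoperative visit date. The rule then reduces to discharge, or to the operative day, unless an end-of-rehabilitation date was recorded. Any surgical injection from the next day on falls into episodic efficacy time.

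Two secondary endpoints are exposed. Annualized consumption for preventing and treating bleeds would include surgical cover. The ABR denominator would include days on which the child was covered for surgery. The episodic and prophylactic summaries, which the SAP presents by regimen, would then rest on different rules.

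The conflict between 5.4.2.1 and 6.6.1.4 is a second route to the same result. Read literally, 6.6.1.4 counts minor-surgery doses whatever the end date.

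**Working it through.** The plan states no figure that depends on this rule, so there is nothing to reproduce. The check has two parts.

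**1. Rule trace.** Take a child on the episodic regimen with same-day minor surgery, no postoperative visit and no rehabilitation date.

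- Period ends: 23:59 on the discharge date, which here is the operative day (SAP 5.4.3).
- Episodic efficacy time restarts: 00:01 the next day (SAP 5.4.2.1).
- A surgical injection at home after that is entered in the diary (Protocol 10.1.2) and falls inside the efficacy period.
- It enters the consumption sum, because only PK doses are removed by type (SAP 6.6, 6.6.1.4).
- The days up to that injection enter the ABR denominator (SAP 7.4.3).

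The same holds for a child who stays episodic after surgery and starts prophylaxis later, since 5.4.3 gives being on the episodic regimen after the surgical period as an example of this branch.

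**2. Size for one child.** All inputs are assumptions for illustration, not document figures or dose proposals:

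- 140 days of episodic time under the SAP rule
- 4 bleeds, each treated with one injection
- 50 IU/kg for every injection
- *n* surgical injections after the period closes, over 14 covered days with no bleed

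Consumption under the SAP = (4 × 50 + *n* × 50) / 140 × 365.25.

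Consumption after the fix = (4 × 50) / (140 − 14) × 365.25 = 200 / 126 × 365.25 = 580 IU/kg/year.

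| *n* | SAP (IU/kg/year) | After fix | Excess |
|---|---|---|---|
| 1 | 250 / 140 × 365.25 = 652 | 580 | +12.5% |
| 3 | 350 / 140 × 365.25 = 913 | 580 | +57.5% |
| 5 | 450 / 140 × 365.25 = 1174 | 580 | +102.5% |

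ABR under the SAP = 4 / 140 × 365.25 = 10.4; after the fix = 4 / 126 × 365.25 = 11.6. The SAP value is 10% lower.

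**Range under other assumptions.** With 2 bleeds, 90, 180 or 365 days of episodic time, and 1 dose over 3 days, 2 over 7 or 4 over 14 (again 50 IU/kg per injection):

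- The smallest consumption excess is at 90 days with 1 dose: 150 / 90 × 365.25 = 609 against 100 / 87 × 365.25 = 420, or +45%.
- The largest is at 365 days with 4 doses: 300 / 365 × 365.25 = 300 against 100 / 351 × 365.25 = 104, or +188%.
- The ABR shortfall runs from 0.8% (2.00 against 2.02; 365 days, 3 covered) to 15.6% (8.12 against 9.61; 90 days, 14 covered).

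**The case against.** **The trigger is assumed.** No section describes home surgical dosing after minor surgery. Protocol 4.2.3 mentions postoperative home treatment only for a bleeding episode. The SAP's planned listing for minor surgery covers dosing on the day of surgery, against 14 days for major surgery, which suggests that little later dosing is expected. This stands, and it limits the size. It does not remove the gap: the protocol has the investigator establish after the day of surgery when the regular regimen resumes, so it allows for a later return.

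**The rule is wider than discharge.** A reader might infer that the SAP simply ends the period at discharge. It does not. It takes the latest of four dates, and a recorded end of rehabilitation would keep later doses inside. Discharge or the operative day governs only by default, mainly after minor surgery.

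**There is no breach.** A reader might also infer that the SAP violates the protocol. Protocol 16.2.2 leaves the efficacy and surgical periods to the SAP, and 10.2.7.1 is a clinical definition. This is a misalignment.

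**Surgical doses are arguably preventive.** They could be said to belong in consumption for preventing and treating bleeds. But SAP 5.4.2.1 takes all surgical periods out of efficacy time, and 6.6.1.4 excludes them for major surgery. The SAP has therefore chosen to keep surgical dosing apart; what is missing is a consistent rule for minor surgery.

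**Conclusion.** The point holds as a minor one. For children on the episodic regimen after surgery, including those who start prophylaxis later, the stated end rule can place surgical injections and covered days in episodic efficacy time. Children on prophylaxis after surgery are handled differently. SAP 5.4.2.1 and 6.6.1.4 also conflict on minor surgery.

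For an affected child the distortion can be large: in the assumed example, +12.5% to +102.5% in consumption and −10% in ABR. Setting the SAP values against 4 × 50 / 140 × 365.25 = 522 would suggest +25%, +75% and +125%. That comparison drops the surgical doses but keeps their 14 days, so it is not the contrast between the two rules.

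The effect needs surgery during episodic treatment, surgical injections after the period closes, and no later recorded date that would hold the period open. The documents give no count, and the number is probably small among about 30 planned children with an optional episodic phase. All efficacy summaries are descriptive. The primary endpoint, inhibitor development, and the sample size are untouched.

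**What to change.** 1. **SAP 5.4.3.** For patients not on prophylaxis afterwards, end the period at 23:59 on the latest of the dates already listed and the date of the last rFIXFc injection recorded with reason surgery for that procedure. Use the return-to-regimen date instead if it is recorded and later; the documents do not show that it is captured, so the injection date should carry the rule.
2. **SAP 6.6.1.4.** Reconcile it with 5.4.2.1 so that minor-surgery periods are also excluded from consumption. Without this, the first change may not take minor-surgery doses out of the consumption total.

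The cost is two sentences and a small programming change. The reason for each injection, including surgery, is already collected (SAP 5.6, 6.6 and 6.6.1.1). The downside is slightly less episodic efficacy time for the children concerned.
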